1 OVERVIEW AND INVESTIGATIONAL PLAN

1.1 STUDY DESIGN AND RANDOMIZATION

This is an open-label, multicenter, Phase II study evaluating the efficacy and safety of SAR566658 administered as a single agent via intravenous infusion in patients with CA6-positive metastatic triple negative breast cancer (TNBC) tumors after at least 1 prior chemotherapy regimen, but no more than 3 for advanced/metastatic disease.

The study will be performed in 2 parts.

Part1: Selection of the dose

Patients with metastatic TNBC overexpressing CA6 (membrane intensity of 2+, 3+ in $\geq 30\%$ of tumor cells) will be randomized to either the 90 mg/m² or the 120 mg/m² cohort, both given at Day 1 and Day 8 of each 3-week cycle. Patients randomized but not treated will be replaced. Study treatment should be initiated no later than 3 calendar days after randomization.

During treatment, safety will be monitored and the risks for predefined safety criteria during the first 2 cycles will be followed and assessed using a Bayesian binomial model. In particular, risks for overdosing and unacceptable toxicity will be assessed as soon as 4 patients treated at the dose level of 120 mg/m² become evaluable for the predefined safety criteria.

The Bayesian model assessing the rate of predefined safety criteria will use dose as a parameter. The elicitation of the prior distribution is derived from the data collected in the first in human (FIH) study (TED10499) at various dose levels and schedules of administration (190 mg/m² q3w, 240 mg/m² q3w, 90 mg/m² D1D8 q3w, and 120 mg/m² q2w).

The elicitation of the prior distribution for the two dose levels is explained in [Appendix A](#).

The decision to stop 1 arm may be taken on the basis of risk of the assessed overdosing (ie, predefined safety criteria rate above 40%) and unacceptable toxicity (ie, predefined safety criteria rate above 60%). The model recommends stopping 1 arm when its overdosing risk or unacceptable toxicity risk will not be controlled at the levels of 25% and 5%, respectively.

Simulations were performed and are presented in [Appendix A](#).

Randomization will be centralized by IVRS/IWRS, stratified on Eastern Cooperative Oncology Group (ECOG) performance status (PS) (0 versus 1). Randomization will be performed when all eligibility criteria are checked and the patient is deemed eligible. Randomization will be stopped at the end of Part 1 and the recruitment will be authorized in Part 2 only when the selected dose is chosen.

The selection of the dose to be continued in Part 2 will be made at the end of Part 1 following the criteria described below:

A preliminary statistical evaluation of antitumor activity by Response Evaluation Criteria in Solid Tumors (RECIST) 1.1 (1) will be done on the first 14 patients treated in each cohort; if at least 2 confirmed responses, partial response (PR) or complete response (CR), in at least 1 cohort are observed then the study can continue in Part 2, if the safety profile is acceptable.

In addition to the efficacy criteria, safety criteria including the number (%) of patients experiencing an eye disorder leading to dose modification or drug discontinuation, or peripheral neuropathy, or a treatment-emergent adverse event (TEAE) leading to dose reduction or drug discontinuation, will be considered.

In case of the efficacy criteria (<2 PR or CR in 14 patients) not being reached for a given dose, then this dose will not be selected.

In case of neither dose reaching the efficacy criteria (<2 PR or CR in 14 patients), then the study will be stopped.

In case of comparable objective response rate (ORR) and safety profiles between 90 mg/m² D1D8 q3w and 120 mg/m² D1D8 q3w, then the lower dose (90 mg/m² D1D8 q3w) will be chosen.

In case of a higher ORR in 120 mg/m² D1D8 q3w and a comparable safety profile to 90 mg/m² D1D8 q3w, then 120 mg/m² D1D8 q3w will be chosen.

In case of a higher ORR in 120 mg/m² D1D8 q3w and a better safety profile with 90 mg/m² D1D8 q3w, then the dose will be selected on the best risk/benefit.

If there are 6 responses or more in the first 14 patients treated at 1 dose, then the study could be stopped for overwhelming efficacy.

Part 2: at the selected dose

Part 2a: Overexpression cohort

The expansion/overexpressing CA6 cohort with an additional 15 metastatic TNBC patients with CA6 overexpression (membrane intensity of 2+, 3+ in ≥30% of tumor cells) will start at the selected dose using the same selection criteria as for Part 1. If at least 7 confirmed responses (PR or CR) are seen among the 29 patients, then the null hypothesis of 12% ORR can be rejected. This test has a 1-sided type 1 error of 10% and 80% power for an alternative hypothesis of 30% response rate.

Part 2b: Mild expression cohort

An additional “mild CA6 expression” cohort of 20 patients with metastatic TNBC with at least 1% positive tumor cells at CA6 membrane intensity ≥1+ and <30% of tumor cells at intensity of 2+, 3+, will be assessed at the selected dose.

1.2 OBJECTIVES

1.2.1 Primary objectives

To evaluate the tumor ORR, according to RECIST 1.1 (Section of SAR566658 in patients with CA6-positive metastatic TNBC):

- **Part 1:** To select the SAR566658 dose based on ORR and safety of 2 dose levels of SAR566658 in patients with metastatic TNBC overexpressing CA6 (membrane intensity of 2+, 3+ in $\geq 30\%$ of tumor cells),
- **Part 2:**
 - **Part 2a:** To demonstrate the activity of SAR566658 based on ORR in patients with metastatic TNBC overexpressing CA6 (membrane intensity of 2+, 3+ in $\geq 30\%$ of tumor cells) treated at the selected dose in an expanded cohort, in addition to the patients treated in Part 1,
 - **Part 2b:** To assess the efficacy of SAR566658 based on ORR in patients with metastatic TNBC and mild CA6 expression (with at least 1% positive tumor cells at intensity $\geq 1+$ and $< 30\%$ of tumor cells at intensity of 2+, 3+) treated at the selected dose in a “mild CA6 expression cohort”.

1.2.2 Secondary objectives

Part 1 and Part 2:

- To assess:
 - Disease Control Rate (DCR), Duration Of Response (DOR), Time To Progression (TTP), Progression-Free Survival (PFS),
 - The impact of ocular primary prophylaxis on the incidence of keratopathies,
 - The PK profile of SAR566658,
 - The potential immunogenicity of SAR566658,
 - The relationship between CA6 expression level in the tumor, and circulating CA6 in blood at baseline, and efficacy outcomes.
- To evaluate the global safety profile

1.2.3 Exploratory objectives

- [REDACTED]
- [REDACTED]

1.3 DETERMINATION OF SAMPLE SIZE

1.3.1 Sample size for Part 1 and Part 2a

It is anticipated that approximately 63 patients will be enrolled into this study.

This study is separated into 2 parts:

Part 1:

Each dose level 90 mg/m² D1D8 q3w and 120 mg/m² D1D8 q3w will include in parallel 14 patients overexpressing CA6.

Based on efficacy and safety (including predefined safety criteria), 1 dose will be selected during the interim analysis at the end of the Part 1 if the futility criteria on ORR is not met and will be continued in Part 2.

Part 2:

Part 2a: An additional 15 patients overexpressing CA6 will be treated in the expansion cohort at the selected dose.

Part 2b: In parallel, 20 patients will be treated at the selected dose in a mild CA6 expression cohort.

1.3.2 Sample size calculation

The sample size calculation is based on efficacy criteria (ORR).

A 2-stage design will be used for the selected dose. It is expected that a beneficial ORR under SAR566658 is of at least 30% (H1). An ORR of 12% (or less) will be considered as clinically non relevant (H0). On the basis of these assumptions, 29 treated patients at the selected dose at the end of Part 2a would be necessary to reject the null response rate of 12% with a global power of 80% and a 1-sided alpha level of 10%. The calculation takes into account 1 interim analysis using a gamma (-2) beta spending function for futility analysis and a Lan-DeMets (OF) alpha spending function in a 1 sample test for a binomial proportion (East version 6.3 using exact computations, Cytel Software, Cambridge, MA).

An interim analysis is planned in Part 1 after 14 patients are treated at each dose. If at least 2 responses over the first 14 patients are observed, then 15 other patients will be treated in Part 2a at the selected dose, if the safety profile is tolerable.

A total of 7 confirmed responses (CR or PR) or more out of 29 patients (14 patients from Part 1 and 15 patients from Part 2a at the selected dose) will be necessary to reject the null hypothesis at the end of the Part 2a expansion cohort.

Sample size determination for the mild CA6 expression cohort (Part 2b).

At the selected dose, the relationship between CA6 expression level and efficacy outcome will be assessed by adding a cohort of 20 patients with mild CA6 membrane staining (at least 1% positive tumor cells at intensity $\geq 1+$ and $< 30\%$ of tumor cells at intensity 2+, 3+).

[figure not shown]
With a sample size of 20 patients, a true response rate above 15% can be rejected with 83% confidence if we observe 0 or 1 response. Moreover, if we observe 7 responses over the 29 patients in the biomarker positive group ($\geq 30\%$, 2+,3+) and ≤ 1 response in the mild CA6 biomarker positive group (CA6 IHC = $< 30\%$ 2+,3+ and $\geq 1\%$, $\geq 1+$), the 1-sided p-value (according to Fisher's exact test) will be around 7%, suggesting an association between biomarker status and ORR.

1.4 STUDY PLAN

Patient pre-screening, screening and enrollment will be centralized by Interactive Voice Response System (IVRS).

Each pre-screened patient will have to sign a pre-screening informed consent which allows the collection of an archived available formalin-fixed paraffin-embedded (FFPE) tumor sample in order to assess centrally for CA6 expression by IHC. A first call to IVRS center will be done prior to sending the slides to central laboratory in order to obtain a pre-screening patient number. For each patient of whom CA6 expression is documented according to the protocol definition, and who have further signed the screening informed consent, the study consists of:

- up to 21-day screening phase prior start of study treatment infusion: the IVRS is called again (2nd call) and the protocol study procedures could start,
- 21-day treatment cycle(s): once the patient has completed the necessary baseline study procedures and is deemed eligible, a third call is given to IVRS in order to enroll the patient. Patients from the Part 1 will be randomized in two treatment arms: 90 mg/m² D1D8Q3w or 120 mg/m² D1D8Q3w stratified by ECOG PS (0 versus 1). Initiation of study treatment should start within 3 calendar days after enrollment is provided,
- an end of treatment visit (30 days after the last study treatment infusion),
- and a follow-up phase every 6-weeks until radiological progression disease, death or withdrawal of consent.

Abbreviations: +ve: positive; D: day; ICF: informed consent form; IVRS/IWRS: Interactive Voice/Web Response System; q3w: every 3 weeks; W: week.

1.5 MODIFICATIONS TO THE STATISTICAL SECTION OF THE PROTOCOL

This section summarizes major changes to the protocol statistical section with emphasis on changes after study start (after the first patient was enrolled). The first patient was enrolled on 2017-03-23.

Table 1 - Protocol amendment statistical changes

Amendment Number	Date Approved	Rationale	Description of statistical changes
1		
To update the sample size in order to use the same methods (exact methods) in the calculation of sample size as the one planned in statistical analyses section for the calculation of the confidence interval of the primary and secondary endpoints.
 
To decrease the power from 85% to 80%, which is acceptable for a phase II study
	
Sample size: The sample size was increased to 29 patients at the selected dose in the overexpression cohort (instead of 28)
 
Number of responses : Number of responses expected at the end of the POC at the selected dose in the overexpression cohort was increased to 7 (instead of 6)
 
Number of responses expected at the end of the interim analysis for overwhelming efficacy was increased to 6 (instead of 5)
 
Power: Power was decreased from 85% to 80%.

1.6 STATISTICAL MODIFICATIONS MADE IN THE STATISTICAL ANALYSIS PLAN

Not applicable.

2 STATISTICAL AND ANALYTICAL PROCEDURES

As a general convention, investigational medicinal product (IMP) administration or study treatment infusion are indifferently used through the document. Both mean SAR566658 infusion.

2.1 ANALYSIS ENDPOINTS

2.1.1 Demographic and baseline characteristics

The baseline value is defined as the last value or measurement available before the first study treatment infusion in the study. This definition applies for all variables unless otherwise specified. For patients randomized and not treated, the baseline value is defined as the last available value obtained up to the date and time of randomization.

All baseline safety and efficacy parameters (apart from those listed below) are presented along with the on-treatment summary statistics in the safety and efficacy sections ([Section 2.4.4](#) and [Section 2.4.5](#)).

Demographic characteristics

Demographic variables include gender (Male, Female), race (White, Black or African American, Asian, American Indian or Alaska Native, Native Hawaiian or Other Pacific Islander, Not reported, Unknown), age in years (quantitative and qualitative variable : <65, [65 - 75[and ≥75 years), ethnicity (Hispanic or Latino, Not Hispanic or Latino, Not reported, Unknown), weight (kg) and BSA, and ECOG PS at baseline.

Medical or surgical history not related to the study disease

Medical and surgical history will include significant prior and concurrent illnesses, using the same definition as the one used in [Section 2.4.5.1](#) for these AEs

This information will be coded using the version of Medical Dictionary for Regulatory Activities (MedDRA) currently in effect at Sanofi at the time of database lock.

Disease characteristics at baseline

Specific disease history will include:

- **Cancer at initial diagnosis:**
 - Time from initial diagnosis to first study treatment administration (in years),
 - Histopathology type,
 - Staging and TNM classification,
 - Scarff Bloom and Richardson histoprognostic factor.

- **Status of the disease at study entry:**
 - measurability of disease (yes / no),
 - number and location of organs with metastases (<3 vs. ≥3) according to the Investigator
- **CA6 expression** (see [Section 2.1.7.1](#))
 - CA6 expression centrally assessed on an archival biopsy
 - Circulating CA6 (centrally assessed)
- **Molecular expression:** Basal-Like status, Luminal A status, Luminal B status, BRCA1 mutation status, BRCA2 mutation status, PD-1 and PD-L1 expression

Prior anticancer therapies

Prior anticancer therapies include previous surgery for cancer, radiation therapy, and systemic anti-cancer treatment (including chemotherapy, immunotherapy, targeted therapy, biologics...).

Systemic anti-cancer treatments and surgery will be respectively coded using the World Health Organization-Drug Dictionary (WHO-DD) and MedDRA using the versions currently in effect at Sanofi at the time of database lock.

Prior anticancer treatment will include:

- Patients with neoadjuvant therapy
- Patients with adjuvant therapy
- Patients with neoadjuvant/adjuvant therapy
- Patients with advanced chemotherapy

For all patients, results to be provided will be:

- Number of patients with previous anthracycline regimen alone,
- Number of patients with previous taxane regimen alone,
- Number of patients with previous anthracycline/taxane regimen.

Among patients with neoadjuvant/adjuvant followed by advanced chemotherapy, patients who relapse within 6 months (<7 months) of end of adjuvant therapy will be identified

For patients with advanced chemotherapy, results to be provided will be:

- number of prior lines (continuous and 1,2,3, >3):
 - Adjuvant/neo-adjuvant therapy will be counted as prior chemotherapy regimen if the patient had a progression/recurrence within 6 months after completion of the treatment,
 - Prior hormonal, biologic (eg, bevacizumab) or immunotherapy, without a cytotoxic agent, are allowed and are not counted as line of therapy

- A chemotherapy line in advanced/metastatic disease is an anticancer regimen that contains at least 1 cytotoxic chemotherapy agent and was discontinued due to progression. If a cytotoxic chemotherapy regimen was discontinued for a reason other than disease progression then this regimen does not count as a “prior line of chemotherapy” unless this regimen was discontinued after treatment response (CR, PR or Stable Disease SD) and disease progression occurring before another line of chemotherapy.
 - best overall response of the last prior advanced chemotherapy
 - time from completion of the last prior advanced chemotherapy to first study treatment administration (months)
 - reason for discontinuation of the last prior advanced chemotherapy
 - duration of last line of therapy
 - prior treatment with eribulin (Yes vs No and if yes detail ; number of prior regimen with eribulin and best response across all the regimen, reason of discontinuation, time from completion to first study treatment administration (months))
 - Disease free survival (DFS) defined as the interval from the first adjuvant chemotherapy date to the last date of relapse, classified into two groups: ≤ 24 months and > 24 months

For prior surgery, number (%) of patients with any prior surgery related to study disease, type of surgery and time from last surgery to first study treatment administration (months) will be provided.

For prior radiotherapy, number (%) of patients with any prior radiotherapy related to study disease, intent and time from last radiotherapy to first study treatment administration (months) will be provided. Adjuvant radiotherapy (yes vs no) will be counted.

Vital signs

See [Section 2.1.4.5](#).

Laboratory exams

See [Section 2.1.4.4](#).

Any technical details related to computation, dates, and imputations for missing dates are described in [Section 2.5.4](#).

EKG

See [Section 2.1.4.6](#).

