7 SELECTION OF PATIENTS

7.1 INCLUSION CRITERIA

- I 01. Metastatic TNBC
- I 02. Patient with measurable disease, as per RECIST 1.1 criteria ([Appendix A](#)).
- I 03. Histologically documented TNBC (either at primary diagnostic or at metastatic site) that is ER-negative and PgR-negative (<1% tumor staining by IHC), and HER2 nonoverexpressing by IHC (0, 1+) or in situ hybridization-negative based on single-probe average HER2 copy number <4.0 signals/cell or dual-probe HER2/CEP17 ratio <2 with an average HER2 copy number <4.0 signals/cell as per ASCO guidelines (2).
- I 04. Patients with CA6-positive disease defined as membrane intensity of 2+, 3+ in $\geq 30\%$ of tumor cells (**Part 1 and Part 2a**) or with at least 1% positive tumor cells at intensity $\geq 1+$ and <30% of tumor cells at intensity of 2+, 3+ (**Part 2b**).
- I 05. Patients received at least 1 prior chemotherapy regimen but no more than 3 for advanced/metastatic disease:
- a) Adjuvant/neo-adjuvant chemotherapy will be counted as a prior chemotherapy for metastatic/recurrent disease if the patient had a progression/recurrence within 6 months after completion of the treatment,
 - b) Prior hormonal, biologic (eg, bevacizumab) or immunotherapy, without a cytotoxic agent, are allowed and are not counted as a line of therapy,
 - c) A chemotherapy line in advanced/metastatic disease is an anticancer regimen that contains at least 1 cytotoxic chemotherapy agent and was discontinued due to progression. If a cytotoxic chemotherapy regimen was discontinued for a reason other than disease progression then this regimen does not count as a “prior line of chemotherapy” unless this regimen was discontinued after treatment response (CR, PR or SD) and disease progression occurred before another line of chemotherapy.
- I 06. Prior anticancer therapy must have contained anthracycline (eg, doxorubicin), if not contraindicated, and a taxane (eg, docetaxel, paclitaxel) in an adjuvant/neo-adjuvant or metastatic setting.
- I 07. Signed written informed consent.

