2.4.4 Analyses of efficacy endpoints

2.4.4.1 Analysis of primary efficacy endpoint(s)

Response rate will be analyzed based on all-treated population as defined in the [Section 2.3.1.1](#).

Overall Response rates will be summarized using counts (n) and percentages (%) and presented with its 2-sided 80% confidence interval using the Clopper and Pearson exact method.

At the end of the Part 2a in the overexpression cohort at the selected dose, an exact binomial test of the null hypothesis that the true response rate is 12% will be performed using a one-sided 0.1 alpha level.

Best Overall Response (BOR) (CR, PR, SD, PD, and NE) will be summarized using counts (n) and percentages by treatment group. At the end of the part1, a summary of BOR by intended dose levels and ECOG stratification factor will also be provided.

For responder patients, a listing with number of prior advanced regimen, prior treatment with anthracycline and/or taxanes (yes/no), prior treatment with eribulin (yes/no), best response to last advanced previous anti therapy, baseline CA6 IHC, baseline circulating CA6, best overall response to SAR566658, duration of response and reason for treatment discontinuation will be provided.

Exploratory analyses

At the end of the Part 2a in the overexpression cohort, ORR will be estimated (with its 80% CI) in several subgroups of patients defined in the table below. A forest plot with estimation of ORR in each subgroup will be provided, if enough patients in each stratum. Depending upon the study results, additional subgroups may be examined, and subgroups with small sample sizes may be pooled to create a larger meaningful subgroup.

Table 3 – Subgroup analyses

Prognostic factor	Description
Age	[18-65[y, [65-75[y, ≥75y
ECOG PS at baseline	0, 1
Any prior eribulin agent	Yes vs No
Mutation BRCA1	Yes vs No
Mutation BRCA2	Yes vs No
Number of organs involved	1,2 ≥3
Number of prior regimen	1,2,3
Bone metastasis only vs visceral metastasis	Yes vs No
DFS	≤24 mo vs >24mo
PD1	Classes to be defined
PDL1	Classes to be defined

Sensitivity analyses of the primary efficacy endpoint

The ORR will also be estimated on the response-evaluable population as defined in [Section 2.3.1.2](#). Depending on the results, exploratory analyses as defined in the [Table 3](#) may also be performed on the response-evaluable population.

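### Prior disease-free survival ends at the last relapse, so a patient with several relapses can fall in the >24 months group although the first came within 24 months

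*SAP*

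**What the plan says.** SAP 2.1.1, under prior anticancer therapies, lists DFS among the items for patients who had chemotherapy for advanced disease ("For patients with advanced chemotherapy, results to be provided will be"). It defines DFS as "the interval from the first adjuvant chemotherapy date to the last date of relapse". The value is then dichotomised at 24 months, with exactly 24 months in the shorter group.

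The split is used again in SAP 2.4.4.1. Table 3, under exploratory analyses, has a DFS row with the levels "≤24 mo vs >24mo", and the text above it says that "ORR will be estimated (with its 80% CI) in several subgroups of patients defined in the table below". The table heads its first column as prognostic factors.

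Neither document redefines prior DFS, gives a version ending at first relapse, or says which relapse counts when there are several. The protocol does not define prior DFS.

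**The concern.** A disease-free interval ends when the disease first comes back. If it runs to the last relapse, time lived with recurrent disease counts as disease-free time, and the value grows with each later relapse.

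This also departs from the SAP's own practice. Duration of response (2.1.3.2.1), time to progression (2.1.3.2.3) and progression-free survival (2.1.3.2.4) all stop at the first progression.

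It can produce conflicting baseline tables too. SAP 2.1.1 separately identifies patients who relapsed within 6 months of finishing adjuvant therapy. Such a patient could carry that early-relapse flag and, because of a later relapse, also be counted as having DFS above 24 months.

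What is at stake is the meaning of one baseline descriptor and of one row of the subgroup forest plot.

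**Working it through.** The documents attach no rate, power or sample size to this variable, so there is no figure to reproduce. The check is one of logic, followed by an illustration of size.

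**Inputs**
- Definition and cut-off: SAP 2.1.1, as quoted above.
- Prior treatment: "Patients received at least 1 prior chemotherapy regimen but no more than 3 for advanced/metastatic disease" (Protocol 7.1), so more than one earlier relapse or progression date is possible.
- Cohort: "29 treated patients at the selected dose at the end of Part 2a would be necessary" (SAP 1.3.2).

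**When the group is wrong.** Let T1 be the time from first adjuvant chemotherapy to first relapse and TL the time to last relapse, so TL ≥ T1. The two end dates give different groups only if T1 ≤ 24 < TL.

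| T1, TL (months, hypothetical) | Group by first relapse | Group by last relapse |
|---|---|---|
| 10, 30 | ≤24 | >24 |
| 23, 25 | ≤24 | >24 |
| 10, 20 | ≤24 | ≤24 |
| 30, 40 | >24 | >24 |

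A move the other way would need TL < T1, which is impossible. The errors therefore cannot cancel. A patient with one relapse has T1 = TL and is unaffected.

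**Effect on the subgroup contrast.** Let pS and pL be the true ORRs in the ≤24 and >24 months groups, and let m be the share of the labelled >24 group that belongs in ≤24. If the moved patients respond like the other early relapsers:
- labelled >24 group: (1 − m)·pL + m·pS
- labelled ≤24 group: pS
- difference: (1 − m)·(pL − pS)

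The difference shrinks by the factor 1 − m and keeps its sign.

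**Illustration of size (assumed inputs).** Among patients with two relapse dates, take T1 and the gap TL − T1 as independent exponentials with medians M1 and Mg. Then

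P(T1 ≤ 24 < TL) = Mg/(M1 − Mg) × (2^(−24/M1) − 2^(−24/Mg)), for M1 ≠ Mg.

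- M1 = 36, Mg = 6: 6/30 × (0.630 − 0.0625) = 0.11
- M1 = 12, Mg = 18: 18/(−6) × (0.250 − 0.397) = 0.44

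For medians of 12 to 36 months to first relapse and 6 to 18 months for the gap, the misplaced share runs from 11% to 44% of multi-relapse patients. The other 56% to 89% are in the right group either way. These medians are assumptions, and the documents do not say how many patients have two or more relapse dates. The percentages therefore cannot be turned into a count.

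**Weight of one patient.** 1/29 = 3.4% of the cohort. Patients without adjuvant chemotherapy have no start date, so fewer than 29 may be classifiable and the weight per classified patient may be larger.

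**The case against.** The best counter-argument is that several relapse dates may be rare. Protocol 7.1 and SAP 2.1.1 describe the end of an advanced line as progression. Apart from the DFS item, the SAP's list of prior therapies uses relapse only for the event after adjuvant treatment. On that reading, successive progressions in metastatic disease are not relapses, and a second relapse date would need something like a treated local recurrence followed by a distant one. If the case report form, which is not among the documents, records a single relapse date, nobody is misplaced. This stands as a limit on size. It does not rescue the definition, because specifying the last date matters only if there can be more than one.

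It is also fair to say that little depends on this variable. It is one of eleven rows in Table 3, reported as estimates without a test, with a forest plot only if strata are large enough and with freedom to pool subgroups. The earliest relapsers are partly visible elsewhere, through the 6-month flag and the subgroup by number of prior regimens. All of this stands.

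Three stronger readings are tempting, but the documents do not support them:
- **Every patient with more than one relapse is misplaced.** Only those with T1 ≤ 24 < TL are.
- **The contrast could reverse.** That needs the moved patients to respond differently from other early relapsers, and nothing in the documents says so.
- **Early relapsers have the worst prognosis here.** Table 3 calls DFS a prognostic factor but gives no direction or size.

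**Conclusion.** The definition is wrong as written: for anyone with an earlier relapse, it gives a value that is not disease-free time. Misclassification at 24 months is possible, one-directional and conditional on the first and last relapse falling on opposite sides of the cut-off. Its consequence is possible blurring of one exploratory subgroup row and of the baseline DFS summary.

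The number affected cannot be derived from the documents and could be zero. The conclusion about the definition needs no assumption. Any effect on results requires that some patients have more than one recorded relapse date. Because DFS enters none of the primary ORR analysis, the interim and dose-selection rules or the sample size, this is a minor point, worth correcting because it costs so little.

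**What to change.** In SAP 2.1.1, end the interval at the date of first relapse instead of the last. If the sponsor really intends the last relapse, keep the calculation but rename the variable in 2.1.1 and in Table 3 so that it is not labelled DFS.

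In the same edit, state how patients with neoadjuvant chemotherapy only, or with no adjuvant chemotherapy, are handled, since the start date is undefined for them.

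The cost is a one-word change plus one sentence, made before programming. The 6-month relapse flag in SAP 2.1.1 suggests that the first relapse date is available, but this should be checked against the case report form. Protocol 10.1.2 asks for oncological history only in general terms and names no relapse date.
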